Sequential nephron blockade, or combination diuretic therapy, with a loop and thiazide-type diuretic is a frequently used strategy to overcome diuretic resistance caused by hypertrophy of the distal convoluted tubule.⁴ In healthy patients, approximately 25% of sodium is reabsorbed proximally at the ascending loop of Henle and 5% of sodium is reabsorbed at the distal convoluted tubule. With increasing doses of loop diuretics, a compensatory increase in sodium reabsorption occurs via the sodium chloride cotransporter at the distal convoluted tubule.⁴ Adding a thiazide-type diuretic, such as metolazone limits this distal reabsorption and therefore restores effectiveness of diuretic therapy. Most studies examining combination diuretic therapy in AHDF are retrospective and evaluate a limited number of patients (1 to 45 patients).⁶⁻¹³ Overall, combination diuretic therapy has been found to be safe and efficacious in increasing urine output and decreasing weight. The most common side effect noted in these studies is hypokalemia. Of the available thiazide diuretics, one has not been found to be more effective than another; however, metolazone is often used due to its potency and long duration of action (up to 20 hours).¹⁴

Based on this observed synergy, combination therapy with furosemide and metolazone is routinely prescribed in patients presenting with ADHF without adequate diuresis from loop diuretics alone. It has been recommended to administer the thiazide-type diuretic one hour

prior to the loop diuretic to allow the thiazide-type diuretic to achieve peak diuretic effect.¹⁵ This practice of pre-administration likely comes from pharmacokinetic and pharmacodynamic data that found the peak diuretic effect of metolazone to be delayed approximately 80 minutes after administration.¹⁶ However, this pharmacokinetic study was performed in two healthy volunteers that were administered metolazone alone. The administration time of metolazone in relation to furosemide dosing has not been studied and is not commented on in the observational and randomized controlled trials looking at combination diuretic therapy. Given the long duration of effect of metolazone, it is unlikely that the delay in peak diuresis would be of clinical importance in terms of desired synergistic effect. Furthermore, the practice of staggering administration times complicates the regimen and puts a burden on nursing staff, especially in units with greater patient to nurse ratios or patients with contact precautions.

Therefore, the practice of administering metolazone 60 minutes prior to loop diuretic therapy increases the complexity for nursing staff and patients without proven clinical benefit. Despite this information, the practice remains common in clinical settings. The purpose of this study is to examine whether administering metolazone 60 minutes prior to furosemide increases urine output compared with administering metolazone and furosemide concomitantly.

Methods:

Study Design:

This will be a prospective, randomized, open-label, active control trial at the University of Maryland Medical Center (UMMC). The objective of this study is to examine whether administering metolazone 60 minutes prior to IV furosemide bolus increases urine output compared with administering metolazone and IV furosemide bolus concurrently. The study has been approved by the institutional review board at UMMC, and written informed consent will be obtained for all patients.

Study Participants:

Adults aged 18 to 89 years are eligible for enrollment if they present within the previous 48 hours with ADHF to the advanced heart failure service at UMMC. ADHF will be defined on the basis of the presence of at least one symptom (dyspnea, orthopnea, cough, or edema) and one sign (rales, peripheral edema, ascites, jugular venous distention, or pulmonary vascular congestion on chest radiography) of heart failure. Additional eligibility criteria are receipt of an oral loop diuretic prior to admission and plan to administer furosemide 120 – 200 mg IV bolus twice daily over the next 24 hours with additional diuresis deemed necessary. Patients are to be excluded if they have cirrhosis, an estimated glomerular filtration rate (GFR) less than 10 mL/min/1.73m2, need for concurrent renal replacement therapy, or if they were prescribed metolazone prior to admission. Non-English speaking patients and patients that could not provide consent and do not have a legally authorized representative to provide consent will also be excluded.

Randomization and Treatment Assignments:

Patients will be randomized in a 1:1 ratio to a pre-dosing strategy (metolazone 5 mg orally dosed 60 minutes prior to furosemide 120 – 200 mg IV bolus) or a concurrent dosing strategy (metolazone 5 mg dosed simultaneously with furosemide 120 – 200 mg IV bolus). All treatment during the 24-hour study period will be open-label at the discretion of the treating physician. Patients enrolled in the study can receive additional IV boluses up to every 6 hours during the 24-hour study period. If per the treating physician, patients required additional doses of metolazone, switch to furosemide IV continuous infusion, titration of IV inotrope or IV vasodilator, or renal replacement during the 24-hour study period, the appropriate therapy will be ordered and the patient will be excluded from the study at that time. Patients will be followed until discharge.

Endpoints:

The primary endpoint will be total urine output (mL) 24 hours post-metolazone dose. The total urine output will be collected and entered into EPIC electronic medical record by nursing staff and the value will be collected by study investigator during chart review. Additional prespecified secondary endpoints that will be assessed 24 hours post-metolazone dose include: net fluid balance (mL), change in weight (kg), change in SCr (mg/dL), proportion of patients with acute kidney injury (AKI) (defined as an increase in SCr by \geq 0.3 mg/dL or \geq 50% from baseline), hypokalemia (K <4.0 mEq/L), hypomagnesemia (Mg <2.0 mEq/L), and hyponatremia (Na 125 - 135 mEq/L 24).

Statistical Analysis:

We calculated that 126 patients would have to be enrolled in order to achieve 80% power to detect an effect size of 500 mL. Given that this was a pilot study, our target patient enrollment will be 30 patients as this was felt to be a feasible number of patients to enroll during the study period. Descriptive statistics will be used to characterize data. When target enrollment is reached, the primary endpoint will be analyzed using student t-test. For other variables and outcomes, data will be analyzed using student t-test or chi-square/Fisher's exact test as appropriate.

References:

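### Excluding randomised patients who are escalated within 24 hours leaves the primary t-test on a subset selected after randomisation, with bias of unknown sign and size

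*Combined protocol and SAP*

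**What the plan says.** The rule is in Methods, Randomization and Treatment Assignments. Patients are allocated 1:1 to pre-dosing or concurrent dosing, after which "All treatment during the 24-hour study period will be open-label at the discretion of the treating physician". The triggers, judged by that physician, are that "patients required additional doses of metolazone, switch to furosemide IV continuous infusion, titration of IV inotrope or IV vasodilator, or renal replacement during the 24-hour" period. When one occurs, "the appropriate therapy will be ordered and the patient will be excluded from the study at that time". Extra boluses are not a trigger: "Patients enrolled in the study can receive additional IV boluses up to every 6 hours during the 24-hour study period". The section ends by saying that follow-up runs to discharge.

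Under Endpoints, "The primary endpoint will be total urine output (mL) 24 hours post-metolazone dose", and "The total urine output will be collected and entered into EPIC electronic medical record by nursing staff".

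Under Statistical Analysis, "When target enrollment is reached, the primary endpoint will be analyzed using student t-test". The section names no analysis population. It does not say how excluded patients' data are handled or whether they are replaced, and it plans no sensitivity analysis.

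**The concern.** Three features combine.

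- The exclusion comes after randomisation, so the assigned timing can influence it.
- Most triggers are further decongestive or haemodynamic support, which is plausibly ordered when output is poor, and output is the endpoint.
- The decision has no stated threshold and is made by someone who knows the arm.

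If one timing works less well and both arms are escalated by the same rule, more of that arm's low-output patients leave and a real difference shrinks. If physicians escalate more readily in one arm, a difference can appear where none exists, or a real one can be inflated or reduced. The expected bias is zero only if escalation is unrelated to output, or if timing has no effect and escalation works identically in both arms. The plan can ensure neither. Every 24-hour secondary endpoint is exposed in the same way.

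**Working it through.** **Inputs from the plan (Statistical Analysis).** Difference 500 mL, power 80%, calculated enrolment 126, target enrolment 30 (about 15 per arm at 1:1).

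**Not in the plan, so assumed.** SD, alpha and sidedness, whether 126 is a total, the escalation rate, and the correlation ρ between the escalation trigger and 24-hour output.

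**Step 1: the plan's own figure.** Take 126 as the total and a two-sided 5% test. Then n per arm = 2(1.960 + 0.842)² × SD² / 500². With SD = 1,000 mL this is 62.8, rounded up to 63, or 126 in total. Solving backwards from 63 per arm gives an SD of 1,002 mL (normal) or 994 mL (t). The figure is therefore plausible at an SD near 1,000 mL, but it cannot be confirmed. Other readings give 1,129 mL (one-sided, 126 total), 1,417 mL (two-sided, 126 per arm) or 1,596 mL (one-sided, 126 per arm).

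**Step 2: model.** A patient is excluded when a trigger score, correlated ρ with output, falls below a cut-off. If a proportion q of an arm is excluded, the mean of those kept is

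μ + ρ × SD × λ(q), with λ(q) = φ(z_q) / (1 − q).

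λ(0.10) = 0.19500, λ(0.20) = 0.34995, λ(0.30) = 0.4967.

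**Step 3: true benefit of 500 mL for pre-dosing, same cut-off in both arms.** With 20% of the concurrent arm excluded, pre-dosing loses q = Φ(−0.8416 − 0.5ρ).

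- ρ = 0.5: q = 13.7%, λ = 0.2549. Observed difference = 500 + 500 × (0.2549 − 0.34995) = about 453 mL.
- ρ = 0.9: q = 9.8%, λ = 0.1921. Observed difference = 500 + 900 × (0.1921 − 0.34995) = about 358 mL.

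| Concurrent arm excluded | ρ = 0.5 | ρ = 0.9 |
|---|---|---|
| 10% | 468 mL | 408 mL |
| 20% | 453 mL | 358 mL |
| 30% | 441 mL | 320 mL |

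At 20%, ρ = 0.3 gives 482 mL and perfect truncation (ρ = 1) gives 328 mL.

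**Step 4: no true effect, different exclusion rates.** False difference = ρ × SD × [λ(q₁) − λ(q₂)], in favour of the arm with more exclusions.

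- 10% vs 20%: 1,000 × 0.15495 × ρ = about 77 mL (ρ = 0.5) to 139 mL (ρ = 0.9); 155 mL at ρ = 1.
- 10% vs 30%: 1,000 × 0.3017 × ρ = about 151 to 272 mL; 302 mL at ρ = 1.

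These scale with the SD. At 1,417 mL, 10% vs 20% gives about 110 to 198 mL (220 mL at ρ = 1).

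**Step 5: true benefit of 500 mL, different exclusion rates.** With 20% excluded from pre-dosing and 10% from concurrent, the result is 500 + 77 to 500 + 139, about 577 to 639 mL. With the rates reversed it is about 423 to 361 mL. The bias can go either way.

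A separate simulation with a true 500 mL, a common cut-off and 20% of the concurrent arm excluded gave 452 mL at ρ = 0.5, in agreement with Step 3. With equal exclusion rates and the same selection in both arms it gave no bias.

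**The case against.** **The plan does not say outright that excluded patients' data are dropped.** This is true, and no bias arises if nobody is escalated. But the rule removes the patient from the study inside the endpoint window, and nothing returns that patient's output to the comparison. Follow-up to discharge does not do so. Dropping is the natural reading.

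**The illustration rests on unsourced inputs.** This stands. The correlation range has no basis in the documents. Permitted boluses keep some poor responders in, and some inotrope or vasodilator titration may be unrelated to diuresis, so the link could be weaker. The SD is back-solved. These points limit what can be said about size, but the flaw remains.

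**The bias is small beside the noise.** With 15 per arm and SD 1,000 mL, the standard error of the difference is 1,000 × √(2/15) = about 365 mL, so 77 to 139 mL is about 0.2 to 0.4 standard errors. This is fair for that scenario. Pilot status explains low power, however, and does not justify a selected comparison. Exclusions also cost precision: power for 500 mL is about 26% at 15 per arm and 22% at 12, under the same assumptions.

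**Output after escalation reflects the added therapy.** This is the strongest point. Suppose escalation adds 1,000 mL. In Step 3 with 20% escalated, the all-randomised difference is 500 − 1,000 × (0.200 − 0.137), about 437 mL at ρ = 0.5. That is more diluted than the 453 mL under exclusion. At ρ = 0.9 it is about 398 mL, which is less diluted than 358 mL. If escalation adds 500 mL, the range is about 469 to 449 mL; if it adds nothing, 500 mL. With no true effect and 10% vs 20% escalated, a 1,000 mL gain shows as 1,000 × 0.10 = 100 mL. Less dilution is therefore not the deciding argument. The all-randomised analysis keeps the comparison as randomised and estimates a defined quantity, the effect of assigning a timing strategy. The subset analysis does neither.

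**Conclusion.** The concern holds and must be fixed. The plan states a rule that selects patients after randomisation, within the primary endpoint window, at the discretion of an unblinded physician, for reasons plausibly tied to the endpoint. Confidence that the flaw exists is high. Its size is unknown, because the documents give neither an escalation rate nor an SD. The worked scenarios move the difference by tens of mL to more than 200 mL, in either direction. They depend on the assumed SD, correlation and exclusion rates. If exclusions are few, or balanced with the same selection in both arms and no timing effect, the bias may be negligible. The plan does not require exclusions to be reported by arm, so a reader could not tell.

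**What to change.** - Replace the exclusion wording. An escalated patient receives whatever therapy the physician orders, stays in the assigned arm, and has 24-hour urine output and the secondary endpoints taken from the chart.
- Define the primary analysis as all randomised patients in their assigned arm. State that it estimates the effect of the timing strategy whatever escalation follows.
- Report escalation within 24 hours by arm, with time and reason, as a secondary endpoint. It must stand beside the primary result because unequal escalation can itself create a difference. The reasons also matter because renal replacement can affect creatinine, weight, fluid balance and electrolytes.
- Keep two supportive analyses: a Wilcoxon test ranking escalated patients lowest, and the comparison without escalated patients. State that both can be biased if escalation thresholds differ by arm. For example, with no effect and escalation unrelated to output, 10% vs 20% escalated moves the Wilcoxon probability index to 0.8 × 0.1 + 0.5 × (0.8 × 0.9 + 0.2 × 0.1) = 0.45 instead of 0.50.

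**Cost.** A wording amendment, plus time and reason of escalation on the chart-review form. Nursing staff already chart output, so no extra visits or patients are needed. The price is the possible dilution described above.

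### Does counting 24 hours of urine from the metolazone dose bias the comparison, because one arm then has 23 hours after furosemide and the other 24?

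*Combined protocol and SAP*

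**What the plan says.** Methods, Endpoints sets one clock for both arms: "The primary endpoint will be total urine output (mL) 24 hours post-metolazone dose". The listed secondary endpoints use the same time point. Nursing staff chart the total, and an investigator later reads it from the record.

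Methods, Randomization and Treatment Assignments defines the arms by dose timing. "Patients will be randomized in a 1:1 ratio to a pre-dosing strategy", in which the patient has "metolazone 5 mg orally dosed 60 minutes prior to furosemide", "or a concurrent dosing strategy (metolazone 5 mg dosed simultaneously with furosemide", each with the same furosemide dose range. The plan calls both arms strategies.

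Two further statements affect what happens inside the window. Under Study Participants, eligibility requires "receipt of an oral loop diuretic prior to admission" and a plan for furosemide as an "IV bolus twice daily over the next 24 hours with additional diuresis deemed necessary". Under Randomization and Treatment Assignments, "Patients enrolled in the study can receive additional IV boluses up to every 6 hours during the 24-hour study period", and "All treatment during the 24-hour study period will be open-label at the discretion of the treating physician".

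The plan contains no furosemide-anchored analysis and does not say why metolazone was chosen as the anchor.

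**The concern.** Furosemide given with metolazone is expected to produce most of the urine. If the clock starts at metolazone, the pre-dosing arm spends its first hour on metolazone alone and its window closes 23 hours after furosemide. The concurrent arm gets a full 24 hours after furosemide. The offset is the randomised 60 minutes itself, so it is present in every patient treated as planned and does not average out.

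The background section asks whether waiting for metolazone to take effect improves the joint response. If the furosemide response were identical in both arms, the primary difference could still be non-zero merely because the windows sit differently around furosemide. A reader could then mistake window placement for an effect of timing, or a real benefit of pre-dosing could be partly hidden. An added analysis of urine 0 to 23 h after furosemide in both arms would seem to settle the matter.

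**Working it through.** **Windows.** Put the first study furosemide at time 0 and take the 60-minute gap as planned.

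| Arm | Metolazone at | Primary window | Hours before furosemide | Hours after furosemide | Total |
|---|---|---|---|---|---|
| Pre-dosing | -1 h | -1 to +23 h | 1 | 23 | 24 |
| Concurrent | 0 h | 0 to +24 h | 0 | 24 | 24 |

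The one-hour offset is real. Total collection time is equal.

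**Decomposition.** In arm means, with no assumption about response:

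primary difference = [difference over 0 to 23 h] + [pre-dosing output from -1 to 0 h − concurrent output from 23 to 24 h].

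The second bracket, the edge term, is all that the placement of the window can contribute.

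**Sign of the edge term.** Both edge hours may be low-output hours.
- The hour before furosemide has metolazone alone. The background's peak effect at about 80 minutes lies beyond that hour, and it comes from two healthy volunteers. However, all patients took an oral loop diuretic before admission.
- Hour 23 to 24 falls 11 to 12 h after the second bolus if twice-daily doses are evenly spaced (assumed), or 5 to 6 h after the last if boluses are given every 6 h.

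The documents do not settle which hour yields more.

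**Size of the edge term.** No urine rate is given, so assume 3,000 to 5,000 mL in 24 h. The average hour is then 3,000/24 = 125 mL to 5,000/24 = 208 mL.
- Equal edge hours: 0 mL.
- One at half the average, the other at the average: 62.5 to 104.2 mL, in either direction.
- Extreme case, nothing in the hour before furosemide and an average hour at 23 to 24 h: -125 to -208 mL.

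**Sampling error.** The plan's own figure is 126 patients for 80% power at 500 mL. It gives no SD, alpha or sidedness, so 126 cannot be rebuilt from stated inputs. Assuming two-sided 5% and SD 1,000 mL, the normal formula gives 2 × (1.960 + 0.842)² × (1,000/500)² = 62.8, so 63 per arm and 126 in all. Solving the t-test version for 63 per arm gives a standardised effect of 0.503, so SD = 500/0.503 = 994 mL.

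At the planned 15 per arm:
- SE = 994 × √(2/15) = 363 mL.
- 95% half-width = 363 × 2.048 = 743 mL.
- Edge term relative to SE: 62.5/363 = 0.17 to 104.2/363 = 0.29. In the extreme case it is 125/363 = 0.34 to 208/363 = 0.57.

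Power for 500 mL at 15 per arm is about 27%. It should not be moved up or down for the edge term. The 500 mL is most naturally read as the difference on the primary endpoint, which already contains the edge term.

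**What a 0 to 23 h window would do.** Counted from furosemide it is the same in both arms. Counted from metolazone it is 1 to 24 h in the pre-dosing arm and 0 to 23 h in the concurrent arm. It also drops the metolazone-only hour, whose output results from pre-dosing.

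**The case for a change.** The strongest argument is that the edge term is systematic. Sampling error shrinks with sample size, and the edge term does not. At 63 per arm the SE would be 994 × √(2/63) = 177 mL, so the same 62.5 to 104.2 mL would be 0.35 to 0.59 SE. A pilot is a good place to learn its size. If one edge hour has an SD of 0.5 to 1.5 times the average hour (assumed), the SD is 62.5 to 312.5 mL. The SE of the edge term is then 62.5 × √(2/15) = 23 mL to 312.5 × √(2/15) = 114 mL, well below 363 mL. The cost is about one timed reading per patient, and a charted total may not be separable afterwards.

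The arithmetic stands, and so does the observation that the plan reports only the sum. The inference does not.

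- The split is an accounting identity and does not isolate a causal effect. Fluid passed in the metolazone-only hour belongs to the pre-dosing strategy and may affect later output. Later boluses, given at the physician's discretion, are not aligned by either clock.
- The precision claimed for the edge term assumes accurate hourly volumes. The plan describes nursing entries read at chart review and mentions no catheter or hourly charting. For patients who void spontaneously, error in void timing could be as large as the term being measured.
- The readings would fall at different times by arm (at furosemide in one, 23 h after it in the other), which adds an arm-specific procedure to an open-label trial.
- The 0 to 23 h difference covers 23 of the same 24 hours, so its precision would be about as poor as that of the total.

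**Conclusion.** The offset exists, but it is not an error. Any fixed 24-hour count must start somewhere. When the randomised factor is the gap between two drugs, no starting point aligns both drugs across arms. Starting at the first dose of each assigned strategy gives equal collection time and keeps everything the strategy causes from that dose onward. This fits a question about which strategy produces more urine.

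Under the assumed 3,000 to 5,000 mL and half-rate scenarios, the edge term is 0 to 104 mL in either direction, at most 0.29 SE with 15 per arm. Even the extreme case stays below 0.6 SE. These sizes rest on an assumed output range and on an SD back-solved from 126 patients, assuming a two-sided 5% t-test. The documents fix neither the size nor the sign.

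The choice of anchor is a fair trade-off, and the alternative analysis would not deliver the separation it promises. If time-stamped entries happen to exist, the authors can describe them in the report. The plan does not need to change for that.

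### AKI is judged only by a creatinine rise at 24 hours, while patients who start renal replacement in that window are excluded, so the AKI proportion may undercount serious renal outcomes

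*Combined protocol and SAP*

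**What the plan says.** Three parts of the Methods bear on this point.

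- **Endpoints.** AKI is a secondary endpoint, reported as the "proportion of patients with acute kidney injury (AKI"). It is "defined as an increase in SCr by" at least 0.3 mg/dL or at least 50% from baseline. Its timing comes from the sentence that opens the list: "Additional prespecified secondary endpoints that will be assessed 24 hours post-metolazone dose include". Change in SCr is in the same list. Renal replacement is neither part of the AKI definition nor an endpoint of its own.
- **Randomization and Treatment Assignments.** For a patient who requires one of several listed therapies, "or renal replacement during the 24-hour study period" being the last of them, "the appropriate therapy will be ordered and the patient will be excluded from the study at that time".
- **Study Participants.** Exclusions at entry include "need for concurrent renal replacement therapy" and "an estimated glomerular filtration rate (GFR) less than 10 mL/min/1.73m2". Any renal replacement during the study would therefore be newly started, and patients with very low renal function can be enrolled.

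The Statistical Analysis section names t-tests and chi-square or Fisher's exact tests. It gives no analysis set for AKI, no rule for data collected before an exclusion, and no rule for an SCr that is missing or affected by dialysis.

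**The concern.** The plan expects that some patients may start renal replacement within 24 hours, and its rule for them removes them before the time at which AKI is assessed. A patient whose kidneys fail soon after dosing is among those whom a renal safety endpoint most needs to capture.

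Taking the exclusion away does not by itself solve the problem. Dialysis lowers SCr, so a retained patient's 24-hour value may meet neither limb of the definition. That patient would then count as a non-event and could also contribute an apparent improvement to change in SCr.

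The trial is open-label and these therapies are started at the treating physician's discretion, so losses need not balance between arms. The comparison of AKI between dosing strategies could be affected, as well as its overall level.

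**Working it through.** The plan gives no figure for AKI to reproduce. Its 126-patient calculation concerns urine output and does not enter here.

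**Inputs**
- Target enrolment is 30 (Statistical Analysis) and allocation is 1:1 (Randomization and Treatment Assignments), so there are 30/2 = 15 per arm.
- Let k be the number of patients in an arm who start renal replacement within 24 hours. The documents do not state it; k = 0 to 2 is assumed.
- Let a be the number of other patients in that arm who meet the SCr criterion. This is also not stated; a = 0 to 4 is assumed.

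**Three ways to score the same arm**
- Excluded, as the treatment section implies: a/(15 − k)
- Retained but scored as non-events: a/15
- Counted as AKI events: (a + k)/15

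| k | a | Excluded | Non-event | Counted |
|---|---|---|---|---|
| 1 | 0 | 0/14 = 0% | 0/15 = 0% | 1/15 = 6.7% |
| 1 | 2 | 2/14 = 14.3% | 2/15 = 13.3% | 3/15 = 20.0% |
| 1 | 3 | 3/14 = 21.4% | 3/15 = 20.0% | 4/15 = 26.7% |
| 1 | 4 | 4/14 = 28.6% | 4/15 = 26.7% | 5/15 = 33.3% |
| 2 | 3 | 3/13 = 23.1% | 3/15 = 20.0% | 5/15 = 33.3% |

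**Size per case**
- Counted against non-event: 1/15 = 6.7 points, whatever a is.
- Counted against excluded, with k = 1: (a + 1)/15 − a/14 = (14 − a)/210. This is 14/210 = 6.7 points at a = 0, 12/210 = 5.7 at a = 2, 11/210 = 5.2 at a = 3 and 10/210 = 4.8 at a = 4.
- With k = 2 and a = 3, the shift from excluded to counted is 33.3 − 23.1 = 10.3 points before rounding, or about 5.1 per case.

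So each case moves an arm's proportion by about 5 to 7 points. With k = 0 nothing moves.

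**The case against.** A reader might infer that a patient who starts renal replacement can never be an AKI event, or that the definition fails whatever the analysis set. The documents do not support either inference:

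- SCr may rise by 0.3 mg/dL or 50% before renal replacement starts, or may still be that far above baseline afterwards.
- The 24-hour wording is also used for cumulative urine output, so it can be read as a window. On that reading an earlier rise would count.
- The documents do not say that values obtained before exclusion are discarded.

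Other parts of the opposing case also stand. AKI is not the only renal endpoint, because change in SCr is listed. Renal replacement may be started to remove fluid in a congested population, so calling every start the most severe renal harm is a clinical reading that the documents do not make. The dialysis-lowered SCr becomes a problem only if excluded patients are brought back. Finally, AKI is one of several secondary endpoints in a 30-patient pilot, where a difference of one event (3/15 against 2/15) gives a Fisher p-value of 1.0.

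The objection does not remove the gap. As written, the exclusion rule takes these patients out before the stated assessment time, and nothing says how they are to be classified. Simply restoring them would correct the denominator without ensuring a correct numerator.

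**Conclusion.** The concern holds as a risk of undercounting. Read together, the two sections make it likely that a patient who starts renal replacement within 24 hours is absent from the AKI proportion. If that patient is retained under the present definition, the event may still be missed.

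The effect is about 5 to 7 percentage points per case in a 15-patient arm, towards fewer recorded events. This assumes full enrolment with equal arms, up to four other AKI events in the arm, and that the affected patient would not otherwise have been counted. How often this would happen is unknown and may be never.

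It does not affect the primary urine-output endpoint's definition, and it would not turn a pilot AKI comparison into a conclusive one. It is worth correcting because the safety description would otherwise omit the cases it should show, and the repair is cheap.

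**What to change.** Reconcile the Endpoints section with the exclusion rule for the renal endpoints. This changes classification and reporting only, not treatment.

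1. **AKI definition.** Count as an event any SCr increase of at least 0.3 mg/dL or at least 50% from baseline, or any start of renal replacement, between the metolazone dose and 24 hours.
2. **Denominator.** Use all randomised and dosed patients, including those who leave study treatment under the exclusion rule.
3. **Reporting.** List renal replacement starts by randomised arm with the reason. Show AKI with and without starts made only for fluid removal.
4. **Change in SCr.** Do not use values taken after renal replacement starts. Report the number of affected patients per arm. Use a value from before renal replacement only if it is post-baseline; otherwise the last value is the baseline itself, which would impute zero change.

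**Cost.** One clause in the endpoint definition and one small listing. A start of renal replacement has to be recognised anyway because it triggers exclusion. The plan does not say that the date and reason are recorded, so the data collection form should ask for them. SCr must also be collected for patients excluded for the other listed reasons. The main downside is that some renal replacement started for fluid removal may count as AKI under the main definition; the second presentation in item 3 shows how much that matters.

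### Hypokalemia, hypomagnesemia and hyponatremia are scored on the 24-hour value alone, so low values present before dosing count as events and blur the comparison (minor).

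*Combined protocol and SAP*

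**What the plan says.** The Endpoints section introduces the list with "Additional prespecified secondary endpoints that will be assessed 24 hours post-metolazone dose include". Two items are changes: "change in weight (kg), change in SCr (mg/dL". Acute kidney injury is a rise in creatinine relative to baseline. The wording then moves straight from a baseline-referenced definition to one without any baseline: "50% from baseline), hypokalemia (K <4.0 mEq/L". The potassium and magnesium definitions read "hypokalemia (K <4.0 mEq/L), hypomagnesemia (Mg <2.0 mEq/L", and sodium of 125 to 135 mEq/L follows in the same form.

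Study Participants requires "receipt of an oral loop diuretic prior to admission" and a plan for high-dose IV furosemide over the next 24 hours. Its exclusions begin "Patients are to be excluded if they have cirrhosis, an estimated glomerular filtration rate (GFR) less than 10 mL/min/1.73m2" and contain no potassium, magnesium or sodium criterion.

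For outcomes other than the primary, Statistical Analysis says only that "data will be analyzed using student t-test or chi-square/Fisher's exact test as appropriate". It mentions no baseline adjustment and no restriction to patients who are normal before dosing.

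The background states: "The most common side effect noted in these studies is hypokalemia".

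**The concern.** Creatinine is examined both as a change and as a baseline-referenced proportion. Potassium, magnesium and sodium appear only as yes/no values at one time point. Read literally, a patient with potassium of 3.6 mEq/L before metolazone and 3.9 mEq/L at 24 hours is a hypokalemia event, although potassium rose.

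Every patient was on an oral loop diuretic before admission, so some low pre-dose values are plausible. How many is not stated. Such events say nothing about the timing of metolazone. They raise the rate in both arms, pull the comparison toward no difference, and leave a reader unable to tell how many events arose after dosing.

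**Working it through.** **The plan's own figure.** The only computed number is 126 patients for 500 mL of urine output at 80% power. The SD and alpha are not stated. With an assumed SD of 1000 mL and two-sided alpha of 0.05, 2 × (1.960 + 0.842)² × (1000/500)² = 62.8, so 63 per arm and 126 in total. The present point does not depend on this figure.

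**Inputs from the documents.** Target enrolment 30 and 1:1 allocation, so 15 per arm; cut-offs as quoted; chi-square or Fisher's exact test for proportions.

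**Assumed inputs, because the documents give none.** q is the share low before dosing; s is the share of those still low at 24 hours, equal in both arms; p is the new-onset risk in patients not low before dosing.

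**Dilution.** The 24-hour proportion in an arm is q·s + (1 - q)·p. The first term cancels between arms, so the expected difference is (1 - q)(p₁ - p₂), whatever the value of s.

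Example with s = 1 and q = 0.4:
- 10% versus 50% becomes 0.4 + 0.6 × 0.1 = 46% versus 0.4 + 0.6 × 0.5 = 70%; the difference falls from 40 to 24 points.
- 20% versus 40% becomes 52% versus 64%; the difference falls from 20 to 12 points and the risk ratio from 2.00 to 1.23.

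With s = 0.5, the second example still has a 12-point difference (44% versus 32%, risk ratio 1.38).

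**Power.** Two-sided Fisher's exact test at 0.05, by full enumeration, 15 per arm, s = 1:

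| q | 10% v 50% | 20% v 40% |
|---|---|---|
| 0 | 54% | 11% |
| 20% | 26% | 6% |
| 40% | 14% | 4% |
| 60% | 8% | 3% |

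**Chance imbalance.** At q = 0.4, the between-arm difference in the number of patients low before dosing has SD √(2 × 15 × 0.4 × 0.6) = 2.7 patients. The counts are equal only about 15% of the time.

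**Counting new-onset events only.** If denominators are fixed at 15(1 - q):
- q = 40% (9 per arm): power is 30% against 14% for all patients in the 10% versus 50% case, and 7% against 4% in the 20% versus 40% case.
- q = 60% (6 per arm): it is 6.4% against 7.6%, and 1.2% against 3.0%.

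If the denominators vary at random instead, the 10% versus 50% case at q = 60% averages about 16%. Restriction can therefore help or hurt, depending on how many patients remain.

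**Information in a yes/no cut.** For a normal variable cut so that a proportion p are events, the fraction kept is φ(z)²/[p(1 - p)], where z is the normal quantile at p: 0.49 at p = 0.2 and 0.64 at p = 0.5. Relative to a baseline-adjusted analysis with an assumed correlation of 0.5, multiply by 1 - 0.5² = 0.75, giving 0.37 and 0.48.

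**The case against.** The proportion below a cut-off at 24 hours is a coherent endpoint, and randomization protects it. Pre-existing low values are balanced in expectation, so there is no systematic bias between arms. That stands. The t-test wording for other outcomes also does not rule out continuous summaries, although none is specified for these electrolytes.

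The steep fall in power needs a 10% versus 50% contrast. Both arms receive metolazone 5 mg and the same furosemide range and differ only in a 60-minute offset, which the background itself thinks unlikely to matter clinically. At 20% versus 40% there is little power to lose. That also stands, and it is why power is not the main argument.

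Some stronger readings are tempting but not supported:
- A reader might infer that the plan masks the main known harm. The background names hypokalemia only, not hypomagnesemia, and as a side effect of combination therapy, which both arms receive.
- A reader might infer that pre-existing events add an identical count to each arm. That is true only on average.
- A reader might infer that most of the information is discarded. The cut alone keeps 49% to 64%; going below half across that range needs the assumed correlation.
- A reader might infer that patients have already had high-dose IV furosemide before metolazone. Study Participants records a plan to give it, not prior receipt.

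What the objection does not answer is that, as written, the endpoint cannot separate events arising after dosing from values already present.

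**Conclusion.** The concern holds as a minor point. Followed exactly, the plan counts pre-dose low values as events for all three electrolytes. The direction is clear when persistence is equal in both arms: the expected difference shrinks by the factor (1 - q). The size cannot be established, because q, s and the event rates are all assumed here, and s = 1 in the power table means that every low value persists. Under those assumptions the loss of power at q = 40% ranges from 40 percentage points (54% to 14%) to 7 (11% to 4%), depending on the effect assumed.

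This is dilution and noise in secondary safety endpoints of a 30-patient pilot. It does not bias the arms systematically and does not touch the primary endpoint. The benefit of a change is mainly interpretability and precision.

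**What to change.** In Statistical Analysis, specify that 24-hour potassium, magnesium and sodium are compared between arms as continuous values by ANCOVA, adjusted for the last pre-dose value. Include all patients, not only those who were normal before dosing.

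Keep the planned all-patient proportions with the cut-offs unchanged. Alongside them, report new-onset proportions among patients who did not already meet the definition before dosing, as descriptive results only, because the smaller denominator can lower power.

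The cost is a few sentences and the abstraction of pre-dose electrolyte values. The plan already takes outcome data from chart review, and change in creatinine already needs a baseline laboratory value, so the added work should be small.
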